9. Subject is on a stable dosage regimen of 1 to 3 AEDs. The daily dosage regimen of concomitant AED therapy must be kept constant for a period of at least 1 week prior to Screening. Vagal nerve stimulation is not counted as medical therapy; however, VNS settings must be kept constant for a period of at least 1 week prior to Screening.
10. Subject is an acceptable candidate for venipuncture.

*Clinical Study Protocol, Section 4.3.2 (Exclusion criteria). Original text:*

Subjects are not permitted to enroll in the study if any of the following criteria are met:

1. Subject is receiving any investigational drugs or using any experimental devices in addition to LCM.
2. Subject meets the withdrawal criteria for the primary study (with the exception of subjects who discontinued due to a dose reduction or status epilepticus), or is experiencing an ongoing serious AE (SAE).
3. Subject has a lifetime history of suicide attempt (including an active attempt, interrupted attempt, or aborted attempt), or has suicidal ideation in the past 6 months as indicated by a positive response (“Yes”) to either Question 4 or Question 5 of the Columbia-Suicide Severity Rating Scale (C-SSRS) at Screening.

*Was revised as follows:*

Subjects are not permitted to enroll in the study if any of the following criteria are met:

1. Subject is receiving any investigational drugs or using any experimental devices in addition to LCM.
3. Subject has a lifetime history of suicide attempt (including an active attempt, interrupted attempt, or aborted attempt), or has suicidal ideation in the past 6 months as indicated by a positive response (“Yes”) to either Question 4 or Question 5 of the Columbia-Suicide Severity Rating Scale (C-SSRS) at Screening.

Subjects who have participated in SP847 or other LCM pediatric clinical studies in epilepsy are not permitted to enroll in the study if any of the following criteria are met:

2. Subject meets the withdrawal criteria for the primary study (with the exception of subjects who discontinued due to a dose reduction or status epilepticus), or is experiencing an ongoing serious AE (SAE).

Subjects who enroll directly into SP848 without previous participation in a LCM clinical study are not permitted to enroll in the study if any of the following criteria are met:

4. Subject has ever received LCM.

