5. Subject has any medical or psychiatric condition that, in the opinion of the investigator, could jeopardize or would compromise the subject’s ability to participate in this study.
6. Subject has a medical condition that could reasonably be expected to interfere with drug absorption, distribution, metabolism, or excretion.
7. Subject has a known hypersensitivity to any component of the investigational medicinal product.
8. Subject is a female of childbearing potential and does not practice an acceptable method of contraception for the duration of the study.

- Medically acceptable contraceptive method includes oral or depot contraceptive treatment with at least 30 $\mu$ g ethinylestradiol per intake (or 50 $\mu$ g if associated with carbamazepine [or other strong enzyme inducers, eg, phenobarbital, primidone, oxcarbazepine]) which must be used in conjunction with a barrier method. Sexual abstinence is also an acceptable method of contraception.
- The subject must understand the consequences and potential risks of inadequately protected sexual activity, be educated about and understand the proper use of contraceptive methods, and undertake to inform the investigator of any potential change in status. Females of childbearing potential must have a negative pregnancy test at the Screening Visit.

9. Subject has an alanine aminotransferase (ALT), aspartate aminotransferase (AST), or total bilirubin level greater than or equal to 2 times the upper limit of normal (ULN), or creatinine clearance less than 50mL/min.
10. Subject has a clinically relevant ECG abnormality, in the opinion of the principal investigator (ie, second or third degree heart block at rest or a QT prolongation greater than 450ms).
11. Subject has hemodynamically significant heart disease (eg, heart failure).
12. Subject has an arrhythmic heart condition requiring medical therapy.
13. Subject has a known history of severe anaphylactic reaction or serious blood dyscrasias.
14. Subject has nonepileptic events, including psychogenic seizures, that could be confused with seizures. If both epileptic and nonepileptic events are present, epileptic events must be distinguished from nonepileptic phenomena.
15. Subject has a history of primary generalized epilepsy.

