*Clinical Study Protocol, Section 2 (Background information). Original text, tenth paragraph:*

SP847 is an open-label, dose-titration, safety, tolerability, and PK study to evaluate LCM as adjunctive therapy in children with uncontrolled partial-onset seizures. Approximately 42 children (aged 1 month to 17 years) with uncontrolled partial-onset seizures on a stable dose regimen of at least 1 but no more than 3 AEDs will be enrolled. The study consists of a Screening Phase, a Treatment Phase, and an End-of-Study Phase. The duration of treatment for an individual subject may be up to approximately 13 weeks. Approximately 200 additional subjects who may participate in other LCM pediatric clinical studies in epilepsy will also be eligible to participate in SP848.

*Was revised as follows:*

SP847 was an open-label, dose-titration, safety, tolerability, and PK study to evaluate LCM as adjunctive therapy in children with uncontrolled partial-onset seizures. The study completed on 26 Aug 2014. Forty-seven subjects (aged 1 month to 17 years) with uncontrolled partial-onset seizures on a stable dose regimen of at least 1 but no more than 3 AEDs were enrolled and treated during the study. The study consisted of a Screening Phase, a Treatment Phase, and an End-of-Study Phase. The duration of treatment for an individual subject was up to approximately 13 weeks.

*Clinical Study Protocol, Section 2 (Background information). Original text, last paragraph:*

SP848 was originally designed as an open-label extension study for pediatric subjects in SP847 with partial-onset seizures. SP848 is now amended to be open to subjects who participate in other LCM pediatric clinical studies in other epilepsy syndromes. In addition, at selected sites, beginning with Protocol Amendment 4, up to approximately 100 eligible pediatric subjects  $\geq 4$  years to  $\leq 17$  years of age with partial-onset seizures (deemed appropriate for treatment with adjunctive LCM) who have not previously participated in a LCM clinical study will be permitted to enroll directly into SP848. The purpose of enrolling these subjects directly into SP848 is to obtain additional long-term safety exposures in the age range of  $\geq 4$  years to  $\leq 17$  years of age; the additional long-term safety data will be included in planned regulatory submissions for LCM as adjunctive therapy for partial-onset seizures.

*Was revised as follows:*

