5. For subject who did not complete a C-SSRS at Screening, subject had actual suicidal ideation in the past 6 months as indicated by a positive response ("Yes") to either Question 4 or Question 5 of the screening version of the C-SSRS. The investigator must immediately refer the subject to a Mental Healthcare Professional and use clinical judgment as to whether to withdraw the patient from the study.

*Was revised as follows:*

All subjects discontinuing treatment with study medication for any reason should taper off medication as described in Section 4.4.1. Whenever possible, these cases should be discussed with the medical monitor prior to withdrawing the subject from the study. All subjects who withdraw from the study due to an AE must be followed until resolution of the event or until the event is considered stable. The following criteria for subject withdrawal from SP848 are outlined below. Additional discontinuation criteria for potential drug-induced liver injury are presented in Section 4.3.3.1.

Participation in this study **must** be discontinued for any of the following reasons:

1. Intolerable AEs, including clinically relevant abnormal laboratory findings that, in the opinion of the investigator, preclude further participation in the study
2. The request of the Sponsor or a Regulatory Agency

3. Subject achieves menarche during the study and does not practice an acceptable method of contraception for the duration of the study (unless sexually abstinent).
4. Subject becomes pregnant, as evidenced by a positive pregnancy test.
5. Subject has a corrected QT interval (QTc) of greater than or equal to 500ms as confirmed by a cardiologist overread on any ECG.
6. Subject develops a second-degree atrioventricular (AV) block while awake or develops a third-degree AV block at any time.
7. Subject is unwilling or unable to continue, or the caregiver/parent/legal guardian is unwilling or unable to allow the subject to continue in the study.
8. Investigator's decision that withdrawal from further participation would be in the subject's best interest.
9. Subject experiences convulsive status epilepticus (if none had occurred prior to study entry) and is compliant with study treatment

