- j For subjects enrolling from EP0060, these assessments should be completed at Visit 1.
- k Blood samples may be drawn at any time post-dosing with LCM.
- l For female subjects of childbearing potential, serum pregnancy tests will be performed at Visit 1, the Early Termination Visit, and the Final Visit. Urine pregnancy tests will be performed at Visits 2, 3, 4, 5, 6, 7, 8, and 9.
- m The Tanner Stage will be performed only for subjects who are pubescent at Visit 1 or who will enter puberty during the course of the study.
- n Lacosamide for taper will be dispensed only for subjects who achieve a dose of LCM  $\ge 6$ mg/kg/day (oral solution [syrup]) or  $\ge 300$ mg/day (tablet). It is recommended that the LCM dose be tapered gradually in weekly decrements of 4mg/kg/day (oral solution [syrup]) or 200mg/day (tablet). A slower taper of 2mg/kg/day (oral solution [syrup]) or 100mg/day (tablet) is permitted, if medically necessary. In case of an emergency, a faster taper is permitted after discussion with the medical monitor, whenever possible.
- o As applicable
- p For all subjects  $\ge 6$  years of age already enrolled, the "already enrolled" version should be completed at the next clinic visit, and the "since last visit" version should be completed thereafter.
- q The C-SSRS assessment should be completed if the Unscheduled Visit is due to an AE.
- r Ongoing AEs from the primary study will be followed, as well as recording of new AEs during the current study.

*Clinical Study Protocol, Section 16.1 (Table 2 Schedule of study procedures for SP848 [Year 2]). Original table:*

REDACTED COPY

This document cannot be used to support any marketing authorization application and any extensions or variations thereof.

**Table 2.** Schedule of study procedures for SP848 (Year 2)

Study SP848	Year 2								Safety Follow-Up
Visit a	V10	TC b	V11	V12	V13/TermV	ETV c	Unsch Visit d	Final Visit e	TC f
Weeks in study	60		72	84	96				
Concomitant medications	X	X	X	X	X	X	X	X	X
Concomitant AEDs	X	X	X	X	X	X	X	X	X
Physical exam (complete)					X	X		X	
Physical exam (brief)	X		X	X			X		
Neurological exam (complete)					X	X		X	
Neurological exam (brief)	X		X	X			X		
12-lead ECG g			X		X	X	X	X	
Blood pressure and pulse	X		X	X	X	X	X	X	
Body weight and height	X		X	X	X	X	X	X	

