SP848 was originally designed as an open-label extension study for pediatric subjects in SP847 with partial-onset seizures. SP848 is now amended to be open to subjects who participate in other LCM pediatric clinical studies, including partial-onset seizures and other epilepsy syndromes. SP848 includes subjects  $\geq 1$  month to  $\leq 18$  years of age since subjects who complete SP847 or another applicable LCM pediatric epilepsy study in subjects  $<18$  years of age may have aged to 18 years old by the time they complete that study and enroll in SP848.

In addition, at selected sites, beginning with Protocol Amendment 4, up to approximately 100 eligible pediatric subjects  $\geq 4$  years to  $\leq 17$  years of age with partial-onset seizures (deemed appropriate for treatment with adjunctive LCM) who have not previously participated in a LCM clinical study will be permitted to enroll directly into SP848. Beginning with local Protocol Amendment 5.2 for sites in Japan, approximately 46 eligible pediatric subjects  $\geq 4$  years to  $\leq 17$  years of age with partial-onset seizures who have not previously received LCM will directly enroll at approximately 9 sites in Japan. Beginning with local Protocol Amendment 5.4 for sites

in China, approximately 60 additional eligible pediatric subjects with partial-onset seizures aged  $\geq 4$  years to  $\leq 17$  years, who have not previously participated in a LCM clinical study, will enroll directly into SP848. The purpose of enrolling these subjects directly into SP848 is to obtain sufficient long-term safety exposures in the age range of  $\geq 4$  years to  $\leq 17$  years of age; the long-term safety data will be included in planned regulatory submissions for LCM as adjunctive therapy for partial-onset seizures in pediatric subjects  $\geq 4$  years to  $\leq 17$  years of age with epilepsy.

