Protocol Amendment 6 allows up to approximately 75 additional eligible pediatric subjects with epilepsy who participated in EP0060 to enroll into SP848. Protocol Amendment 8 allows an enrollment increase from 75 to 100 eligible pediatric subjects  $\geq 1$  month to  $\leq 17$  years of age with epilepsy who participated in EP0060 to enroll in SP848 in order to reflect EP0060's inclusion of subjects down to 1 month of age. In addition, subjects already enrolled in SP848 may participate in EP0060, if eligible, and then resume participation in SP848. These subjects may either voluntarily choose to have an iv LCM infusion even though they are capable of taking oral LCM or require iv LCM infusion due to a medical reason or procedure (ie, unable to take oral LCM).

Approximately 200 subjects who may participate in other LCM pediatric clinical studies in epilepsy will be eligible to participate in SP848. In total, up to approximately 400 subjects may be eligible to participate in SP848.

*Clinical Study Protocol, Section 1 (Summary). Original text, seventh and eighth paragraphs:*

The primary variables for assessment of safety and tolerability are:

- Adverse events (AEs) reported spontaneously by the subject and/or caregiver or observed by the investigator
- Subject withdrawal due to AEs
- Hematology, blood chemistry, endocrinology, and urinalysis parameters
- 12-lead electrocardiograms (ECGs)
- Vital sign measurements (blood pressure and pulse)
- Physical and neurological examination findings
- Body weight, height, and calculated body mass index (BMI)
- Tanner stage (if applicable)
- Plasma concentrations of LCM (for population PK analysis) and concomitant AEDs
- Achenbach Child Behavior Checklist (CBCL) for children 18 months and older (CBCL/1½-5 and CBCL/6-18) assessing behavior
- Bayley-III scales for children  $<18$  months of age at time of enrollment (applicable only to subjects enrolled in English-speaking countries)

- Cognitive function assessments (Behavior Rating Inventory of Executive Function® [BRIEF®]/BRIEF®-Preschool Version [BRIEF®-P]) (if applicable)

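### Withdrawal criterion 3 depends on menarche during SP848, so a girl already post-menarcheal at entry who stops contraception meets no contraception-specific mandatory stop before a positive pregnancy test

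*Protocol*

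**What the plan says.** The current withdrawal list is the Section 4.3.3 text printed under Section 17.6 (Protocol Amendment 6). Mandatory criterion 3 is: "Subject achieves menarche during the study and does not practice an acceptable method of contraception for the duration of the study (unless sexually abstinent". Criterion 4 requires withdrawal on a positive pregnancy test. Mandatory criterion 8 rests on the investigator's view of the subject's best interest, and discretionary criterion 3 covers noncompliance with study procedures or medication. Amendment 7 only renumbers exclusion criteria. In this area Amendment 8 revises only the liver-injury subsection, 4.3.3.1.

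The one other contraception rule in the lists shown is Exclusion 8 (Section 4.3.2, printed under Section 17.4): "Subject is a female of childbearing potential and does not practice an acceptable method of contraception for the duration of the study". It also requires that the subject "undertake to inform the investigator of any potential change in status". It stands under the heading "Subjects who enroll directly into SP848 without previous participation in a LCM clinical study are not permitted to enroll in the study" and therefore applies to direct enrollers.

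Rollover subjects face Exclusions 1 and 3 (all subjects), Exclusion 2 (the primary study's withdrawal criteria, or an ongoing serious adverse event) and, if they were enrolled directly in EP0060, Exclusion 21. None mentions contraception.

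The protocol expects fertile rollover subjects. Section 1 (Amendment 8 text) says that subjects from earlier studies "may have aged to 18 years old by the time they complete that study and enroll in SP848". The footnote to Table 16-1 states: "For female subjects of childbearing potential, serum pregnancy tests will be performed at Visit 1, the Early Termination Visit, and the Final Visit". Urine tests follow at Visits 2 to 9 and, in Table 16-2, at Visits 10 to 13.

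**The concern.** The same lapse in contraception has different consequences depending on when menarche occurred. A girl whose menarche falls a week after Visit 1 must be withdrawn if she does not use contraception. A girl whose menarche came a week before Visit 1, or years before, need not be. The rule thus reaches the newly fertile subject and omits the one already fertile at entry. For the latter, the first mandatory stop that is specific to contraception or pregnancy is a positive test, by which time fetal exposure has begun. This is a patient-safety point. It does not touch any endpoint, estimate or error rate.

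**Working it through.** No power or error-rate calculation applies. The check is to rebuild the current lists from Amendments 4 and 6, apply the later logged changes, and ask which rule reaches each group.

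| Subject | Contraception rule at entry, in the criteria shown | Mandatory withdrawal for a lapse during SP848 |
|---|---|---|
| Menarche during SP848, either route of entry | Not yet relevant | Criterion 3 |
| Direct enroller, post-menarcheal at entry | Exclusion 8: commitment for the whole study, plus duty to report a change | None specific before criterion 4 |
| Rollover, post-menarcheal at Visit 1 | None in the SP848 lists; Exclusion 2 may bring in a parent-study rule (not shown) | None specific before criterion 4 |

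Criterion 3 joins two conditions, and the first (menarche during the study) is false for rows two and three whatever happens later. Exclusions 2 and 8 are both eligibility criteria. Exclusion 8 looks forward over the whole study, but neither is repeated as a withdrawal criterion.

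**How soon a pregnancy would be detected.** Scheduled tests follow the clinic visits at Weeks 0, 4, 8, 12, 20, 28, 36, 44, 52, 60, 72, 84 and 96. The gaps are 4 weeks up to Week 12, 20 − 12 = 8 weeks from there to Week 60, and 72 − 60 = 12 weeks after that. With the ±7-day window at each of two consecutive visits, the longest scheduled gap is 12 + 1 + 1 = 14 weeks. Section 5.21 also permits remote visits during the pandemic.

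**How many are affected.** The document does not settle even the size of the rollover pool. The inputs are SP847 ("Forty-seven subjects (aged 1 month to 17 years) with uncontrolled partial-onset seizures"), other studies ("Approximately 200 subjects who may participate in other LCM pediatric clinical studies in epilepsy will be eligible to participate in SP848"), up to 100 from EP0060, about 100 direct enrollers, about 46 in Japan, about 60 in China, and a total of about 400 (Sections 1, 2 and 12.2).

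- EP0060 inside the 200: 47 + 200 = 247 rollovers.
- EP0060 on top of the 200: 47 + 200 + 100 = 347.
- Total of 400 binding and the three direct groups separate: 400 − (100 + 46 + 60) = 194.

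The total does not choose between these. Even the 247 reading gives 247 + 100 + 46 + 60 = 453, or 247 + 100 + 60 = 407 if Japan's 46 lie within the 100. No source gives sex or menarcheal status, and the pool includes boys and infants from 1 month of age.

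**The case against.** The strongest reply is that much of the protocol is out of sight. Part 1 is not shown, and a contraception instruction for rollover subjects could stand in the body text. Exclusion 2 may already bar, through the parent study's withdrawal criteria, a girl not using contraception at entry. Criterion 3 could then have been meant as a complement for girls who become fertile later. This stands as a limit: a gap at entry cannot be established. It does not answer a lapse after Visit 1, because Exclusion 2 operates at entry and treatment may last about 2 years.

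A second reply is that the backstops are substantial: a serum test at Visit 1, urine tests at Visits 2 to 13, mandatory withdrawal on pregnancy, and investigator discretion. This also stands, and it keeps the point minor. The tests, however, detect pregnancy rather than prevent it, and a discretionary ground about study procedures does not clearly reach contraception where none is prescribed.

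Third, in a study meant partly to continue access to lacosamide, leaving a lapse to the investigator is defensible. That is fair as policy, but the sponsor already mandates withdrawal for the same lapse after menarche on study, and the text shown gives no reason for the difference.

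A reader might infer that the gap belongs to rollover subjects alone and that Exclusion 8 closes it for direct enrollers. The lists do not support that: Exclusion 8 secures a commitment at entry, but no mandatory withdrawal criterion names its breach.

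**Conclusion.** The point holds as a minor patient-safety correction. In the criteria shown, a girl post-menarcheal at entry who stops contraception during SP848 meets no contraception-specific mandatory withdrawal criterion. The gap is widest for rollover subjects, who lack even the entry commitment and reporting undertaking of Exclusion 8.

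Two stronger readings should be avoided. One is that rollover subjects have no contraception obligation at all; Part 1 and the parent protocols could contain one. The other is any figure for the number of girls affected: the rollover pool could be 194, 247 or 347 on different readings, and any share who are post-menarcheal girls would be invented.

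The conclusion assumes that the exclusion and withdrawal lists, as reprinted in Amendments 4 and 6 and changed by later logs, are complete, and that the study named in criterion 3 is SP848.

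**What to change.** At the next amendment, change the opening condition of mandatory criterion 3 so that it applies to a subject who is a female of childbearing potential, including one who reaches menarche during the study, and who after counselling still does not use acceptable contraception. Keep the rest of the sentence, including the abstinence exception. This covers rollover and direct enrollers alike.

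The cost is the wording of one criterion and a counselling conversation, with no added visit or test. The downside is that a few subjects who decline contraception after counselling would have to taper and lose study lacosamide, which cuts against the objective of continued access. Counselling should therefore be written into the criterion itself.
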